6.1.2 Secondary Objectives

- Evaluate the effect of TU-100 compared with placebo on measures of early GI recovery related outcomes including hospital LOS (see [Section 6.2.2](#))
- Evaluate the safety and tolerability of TU-100 compared with placebo after daily in-hospital dosing (up to 10 days)
- Evaluate TU-100 compared with placebo with regards to the incidence and severity of hepatobiliary AEs

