6.2.4 Exploratory Endpoints

Other exploratory endpoints of this study are as follows:

- Subject-reported (electronic diary [eDiary]) occurrence of nausea, vomiting and/or retching, and abdominal bloating per day
- Subject-reported (eDiary) number of episodes of vomiting and/or retching per day
- Subject-reported (eDiary) bothersomeness of nausea and abdominal bloating by day
- Incidence and severity of nausea, vomiting/retching, abdominal bloating based on spontaneous AE reporting from safety database
- Postoperative antiemetic rescue
- Postoperative complications
 - Prolonged POI:
 - Minimal incision BR (laparoscopic or robotically-assisted or hand-assisted): Unresolved POI by postoperative Day 3
 - Laparotomy (open) BR: Unresolved POI by postoperative Day 5
 - Note: POI = primary POI (i.e., POI that is not secondary to surgical complication, such as anastomotic leak, abscess formation, or sepsis etc.)
 - Recurrent POI (that prolongs hospital stay or results in readmission – based on investigator assessment)
 - Surgical site infection
 - Anastomotic leak
 - Early postoperative mechanical small bowel obstruction (EPSBO) (Confirmed by the presence of a transition point between dilated and decompressed bowel demonstrated on abdominal imaging)
- Time to discontinue intravenous (IV) fluids
- Time to transition to oral analgesics
- Hospital readmission (within 7 days and within 30 days of discharge)

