7 INVESTIGATIONAL PLAN

7.1 Description of Overall Study Design and Plan

This multicenter, randomized, double-blinded, placebo-controlled study will evaluate the effect of TU-100 on resolution of POI in subjects undergoing open or minimally invasive BR. Straight, hand-assisted, and robotically-assisted laparoscopic approaches are allowed. Subjects undergoing major abdominal resective intestinal surgeries (BRs; e.g., small BR, large BR, rectal resections [low anterior resection], total colectomy with ileo-rectal anastomosis) will be eligible for enrollment.

Subjects will be screened up to 28 days before their planned surgery and will be randomized 1:1:1 (TU-100 15 g/day: TU-100 7.5 g/day: placebo) on postoperative Day 1 before the first dose of study medication. Subjects will be stratified based on surgical approach (open versus laparoscopic). After randomization, subjects will receive a total daily dose of TU-100 15 g, TU-100 7.5 g, or matching placebo TID until hospital discharge or \leq 10 days (whichever is earlier). All subjects will be treated with study medication as adjunct to an enhanced recovery (i.e., ERAS) pathway for GI recovery, the components of which are standardized, to the extent possible, by the protocol (SOC) (See [Section 7.2](#)).

Efforts will be made to obtain 134 subjects in each of the 3 treatment groups for a total of 402 subjects.

[figure not shown]
There will be 2 independent committees with additional safety oversight. Each will have a formal charter and their specific roles will be discussed within this protocol.

- Data and safety monitoring board (DSMB; clinical trial safety oversight)
- Clinical endpoint adjudication committee (CEAC; for assessment of hepatobiliary AEs)

This study follows the FDA guidance on the conduct of clinical trials and statistical considerations for clinical trials during the COVID-19 pandemic as necessary.

[Figure 1](#) presents the study design.

Figure 1. Study Design

- Abbreviations: R = Randomized; S = Surgery.
- ^a Treatment will be for a maximum of 10 days while subjects are hospitalized. If a subject is discharged before postoperative Day 10, study medication will be discontinued upon hospital discharge.

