9 TREATMENTS

9.1 Details of Study Treatments

All dosing of study drug will be in the hospital (no outpatient dosing).

All study medication will be blinded.

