10.2.4 Follow-up Period

Follow-up contact (10 to 14 days after last dose of study drug)

All subjects will be contacted via telephone (or in-person if still in the hospital) within 10 to 14 days after the last dose of study medication for follow-up that will include:

- Record concomitant medications
- Monitor AEs
- Review of data for hepatobiliary AEs
- Monitor prespecified postoperative complications
- Determine whether hospital readmission occurred and reason for readmission

A certified letter will be sent to any subject not contacted after 3 attempts by telephone.

Follow-up visit (30 days + 15 days after hospital discharge)

All subjects are to return for a follow-up visit 30 days (+ 15 days). Procedures to be conducted at this visit include:

- Perform physical examination, including weight. Any clinically relevant physical abnormalities (with the exception of surgical scars) that were not present at screening should be recorded as AEs.
- Record vital signs (blood pressure, heart rate, respiratory rate, and temperature)
- Record concomitant medications
- Monitor AEs
- Monitor prespecified postoperative complications
- Determine whether hospital readmission occurred and reason for readmission
- If elevated at discharge and trending down, then liver tests will be completed at the 30-day follow-up visit. If a subject remains in the hospital for an AE of elevated tests, then levels will be followed until resolution.

If a patient does not return for a scheduled visit, all necessary measures should be taken to contact the patient and document the patient's outcome.

Reasonable efforts should be made to contact subjects who are lost to follow-up. A certified letter will be sent to any subject not contacted after 3 attempts by telephone. These efforts must be documented in the subject's file.

Exceptional measure for COVID-19

Depending on the COVID-19 situation (and/or to reduce burden of patient travel as needed), measures below may be considered for the 30-day follow-up visit.

- Window for the 30 day follow-up can be extended to +15 days after hospital discharge.
- If subject is unable to come to clinic for in-person visit, then performing LFT laboratory tests (if needed) at a local hospital, or regional independent laboratory located near the subject will be considered. Local laboratory results should be documented in subject's file.

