12.6 Adverse Events

12.6.1 Adverse Events

An AE is any symptom, physical sign, syndrome, or disease that either emerges during the study or, if present at screening, worsens during the study, regardless of the suspected cause of the event. All medical and psychiatric conditions (except those related to the indication under study) present at screening will be documented on the medical history eCRF. Changes in these conditions and new symptoms, physical signs, syndromes, or diseases should be noted on the AE eCRF during the rest of the study. Clinically significant laboratory abnormalities should also be recorded as AEs.

Subjects will be instructed to report AEs at each study visit. All AEs are to be followed up until resolution or a stable clinical endpoint is reached. Each AE is to be documented on the eCRF with reference to date of onset, duration, frequency, severity, relationship to study drug, action taken with study drug, treatment of event, and outcome. Furthermore, each AE is to be classified as being serious or nonserious. Changes in AEs and resolution dates are to be documented on the eCRF.

For the purposes of this study, the period of observation for collection of AEs extends from the time the subject gives informed consent until the follow-up visit. Follow-up of the AE, even after the date of therapy discontinuation, is required if the AE persists until the event resolves or stabilizes at a level acceptable to the investigator.

When changes in the intensity of an AE occur more frequently than once a day, the maximum intensity for the event should be noted. If the intensity category changes over a number of days, then those changes should be recorded separately (with distinct onset dates).

The DSMB will be periodically reviewing safety data.

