14.6.2 Adverse Events

The incidence of all TEAEs (events with onset dates on or after the start of the study drug) will be tabulated by treatment received. All reported AEs will be classified by system organ class and preferred term using the Medical Dictionary for Regulatory Activities (MedDRA). The incidence of TEAEs will be included in incidence tables. All AEs will be listed by subject, along with information regarding onset, duration, relationship and severity to study drug, action taken with study drug, treatment of event, and outcome. An overview of TEAEs, which includes subject incidence of TEAEs, treatment-related TEAEs, TEAEs by severity, SAEs, deaths, AEs leading to discontinuation, and independently adjudicated hepatobiliary AEs will be presented. Events with missing onset dates will be included as treatment-emergent. If a subject experiences more than 1 occurrence of the same AE, the occurrence with the greatest severity and the closest association with the study drug will be used in the summary tables.

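### The TEAE definition in Section 14.6.2 has no end boundary, so off-drug events up to 30 to 45 days after discharge are pooled with on-drug events; a prespecified treatment-period column and a stop-date exception for missing onsets would correct this

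*Combined protocol and SAP*

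**What the plan says.** Section 14.6.2 defines the counting rule: "The incidence of all TEAEs (events with onset dates on or after the start of the study drug) will be tabulated by treatment received". The start is the first dose and no end is given. The only upper limit comes from AE collection in Section 12.6.1, where "the period of observation for collection of AEs extends from the time the subject gives informed consent until the follow-up visit". Section 10.2.4 places that visit after discharge: "All subjects are to return for a follow-up visit 30 days (+ 15 days").

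Exposure is much shorter. Figure 1 in Section 7.1 notes that "Treatment will be for a maximum of 10 days while subjects are hospitalized", and Section 9.1 adds "All dosing of study drug will be in the hospital (no outpatient dosing"). The matching secondary objective in Section 6.1.2 is tied to that period: "Evaluate the safety and tolerability of TU-100 compared with placebo after daily in-hospital dosing (up to 10 days").

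Two further items use the same rule or depend on it. Section 6.2.4 lists an exploratory endpoint with no time limit: "Incidence and severity of nausea, vomiting/retching, abdominal bloating based on spontaneous AE reporting from safety database". Section 14.6.2 also states: "Events with missing onset dates will be included as treatment-emergent".

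Section 14.6.2 additionally plans an overview (treatment-related TEAEs, severity, SAEs, deaths, AEs leading to discontinuation, adjudicated hepatobiliary AEs) and a listing of every AE with its onset. It plans no table restricted to the treatment period.

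**The concern.** The secondary objective asks how the drug is tolerated during a short in-hospital course. The table that answers it also counts, with equal weight, first onsets several weeks after the last dose. In a surgical population some of those late events will have nothing to do with study drug and can be expected at similar rates in all three arms. Adding them narrows the difference between arms and pulls the risk ratio toward 1.

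The severity summaries are exposed too. Where a subject has the same AE more than once, Section 14.6.2 keeps the most severe occurrence, so a severe recurrence after discharge would replace a mild on-drug episode.

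The counting window also ends relative to discharge. Time to the discharge order and length of stay are efficacy endpoints in Section 6.2.2. If the drug shortened stay, treated subjects would be counted over a shorter period from first dose.

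The missing-onset rule is a smaller, separate matter. AE collection begins at consent, before surgery and so before first dosing on postoperative Day 1. An event that was over by then could still enter the TEAE tables.

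**Working it through.** The plan states no AE rate, tolerability difference or safety power, so there is no figure to reproduce. The check has three parts.

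**1. Share of the window that is off drug**

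Inputs: follow-up 30 to 45 days after discharge (Section 10.2.4); dosing at most 10 days (Section 7.1); anticipated stay of at least 4 calendar days (Section 8.1), taken here as 4 dosing days for illustration. Share off drug = follow-up days / (follow-up days + dosing days), taking dosing to stop at discharge.

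- 4 dosing days: 30/34 = 88% to 45/49 = 92%.
- 10 dosing days: 30/40 = 75% to 45/55 = 82%.

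These are shares of calendar time. They are not shares of events, because events after surgery need not be spread evenly.

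**2. Effect on the tabulated difference**

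Let p be the on-drug incidence in an arm and q the off-drug incidence. Assume q is equal across arms and independent of on-drug events. Then:

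- Tabulated incidence = 1 - (1-p)(1-q).
- Tabulated risk difference = (p_active - p_placebo)(1-q).

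The difference therefore shrinks by exactly the factor (1-q), whatever the on-drug rates are. The risk ratio depends on the rates. All rates below are assumptions, chosen to show a range:

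| q | Factor | 20% v 35% becomes | Difference (points) | RR | 5% v 15% becomes | Difference (points) | RR |
|---|---|---|---|---|---|---|---|
| 0 | 1.00 | 20.0 v 35.0 | 15.0 | 1.75 | 5.0 v 15.0 | 10.0 | 3.00 |
| 2% | 0.98 | 21.6 v 36.3 | 14.7 | 1.68 | 6.9 v 16.7 | 9.8 | 2.42 |
| 5% | 0.95 | 24.0 v 38.25 | 14.25 | 1.59 | 9.75 v 19.25 | 9.5 | 1.97 |
| 15% | 0.85 | 32.0 v 44.75 | 12.75 | 1.40 | 19.25 v 27.75 | 8.5 | 1.44 |
| 30% | 0.70 | 44.0 v 54.5 | 10.5 | 1.24 | 33.5 v 40.5 | 7.0 | 1.21 |

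Worked example, 20% v 35% with q = 15%: placebo 1 - 0.80 × 0.85 = 0.32; active 1 - 0.65 × 0.85 = 0.4475; difference 0.1275 = 0.15 × 0.85.

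A low q is plausible for one preferred term, and the risk difference then barely moves, although the ratio for an uncommon term still falls. A larger q is plausible for any TEAE or for a system organ class, which is where the dilution would be visible.

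**3. Missing onset dates, rule by rule**

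- Section 14.4, partial start date: a missing day or month is imputed. If the imputed start falls after a complete stop date, the start is reset to the stop date. An event that ended before first dose therefore stays outside the TEAE count.
- Section 14.4, wholly missing start date: no imputation, so the stop-date check never applies.
- Section 14.6.2: missing onset means treatment-emergent, without exception.

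An event with a wholly missing start and a known stop before first dose is therefore counted as a TEAE, although the available data show that it was not one.

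**The case against.** The strongest reply is about size. The documents give no off-drug rate, and Section 7.2 describes the hospital stay as the time of highest risk for delayed GI recovery and its complications. Off-drug rates for GI symptoms may therefore be low, and at 2% to 5% the risk difference keeps 95% to 98% of its value. This stands.

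Other parts of the plan limit the damage. AEs that lead to stopping study drug arise while it is being given. Hepatobiliary events have their own adjudicated analysis (Section 14.7.1), for which long follow-up is an advantage. In-hospital nausea, vomiting and bloating are captured daily by eDiary (Sections 6.2.4 and 11.3), so the spontaneous-AE version is supplementary. These points stand. Treatment-related TEAEs are a weaker safeguard: in Table 4 the possibly-related category includes events whose link to study drug looks unlikely but cannot be excluded.

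Onset dates are listed, so a treatment-period table could be produced later from the same data. That is true, but a boundary chosen after unblinding would be post hoc. Section 14.1 also leaves analytical details and data displays to a SAP. No SAP text on this point is in the document, so a later SAP may already close the gap.

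A reader might infer that, because about 90% of the window can be off drug, the tables would hide any tolerability difference. The documents do not support that. The 90% is calendar time, the shrinkage is (1-q) with q unknown, and several planned summaries are largely unaffected. Nor can the effect be stated as lost power, since Section 14.6.2 plans tabulation and no safety test.

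**Conclusion.** The gap is real and modest. Section 14.6.2 sets no end to treatment emergence and plans no treatment-period table, although the objective concerns in-hospital dosing. Under similar and independent off-drug event rates across arms, the tabulated risk difference is reduced by a proportion q: 2% at q=2%, 5% at 5%, 15% at 15%, 30% at 30%. The actual q cannot be taken from the documents. If the drug had delayed effects, the equal-rates assumption would fail and the longer window could reveal a difference, which is a reason to keep the all-period table.

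It might also be inferred that the main table should be cut off just after the maximum dosing period, for example at postoperative Day 11. The documents do not require that. For a subject dosed for 4 days such a window is itself 7/11 = 64% off drug, and nothing in the text justifies a particular lag.

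The missing-onset misclassification follows directly from the wording of Sections 14.4 and 14.6.2. It needs a wholly missing start together with a stop before first dose. The documents give no frequency for this, and it is probably rare. Both points are inexpensive improvements to reporting; neither is an error in a stated figure.

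**What to change.** In Section 14.6.2, or in the SAP before unblinding:

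1. Keep the all-period TEAE table as it is.
2. Beside it, prespecify a treatment-period column with a stated end boundary, and a later-onset column. The sponsor should choose and justify the boundary. A fixed postoperative day is one option, because the window then does not depend on discharge, which is itself an endpoint.
3. Apply the same split to the spontaneous-AE nausea, vomiting/retching and bloating endpoint in Section 6.2.4.
4. Add an exception to the missing-onset sentence: such events count as treatment-emergent unless the stop date is before the first dose. Events with neither date known stay treatment-emergent.

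The cost is a wording change and one or two extra columns per AE table. No new data are needed, because onset dates are already recorded and collection runs to the follow-up visit. Nothing is dropped from the existing displays.

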14.6.3 Prior or Concomitant Medications

Medications will be coded by the World Health Organization Drug Dictionary to Anatomical Therapeutic Classification (ATC) and preferred drug name. Prior and concomitant medications will be summarized by ATC level and preferred drug name and listed. Post-operation opioid consumption (mg morphine equivalents; [APPENDIX_02](#)) will be summarized descriptively. Summary tables will be provided for concomitant medications initiated during the study period.

14.6.4 Clinical Laboratory Parameters

Clinical safety laboratory tests will be conducted by local or central laboratories. Summary statistics for actual values and for changes from baseline will be tabulated for hematology and chemistry (with a focus on liver transaminases and LFTs) results by treatment group. Clinical laboratory data and vital signs will be summarized using descriptive statistics, including mean values and mean change from baseline values, as well as numbers of subjects with values outside limits of the normal range at each time point. Shift tables for clinical laboratory parameters will be provided to assess the changes in laboratory value from baseline to post-baseline visits. Normal reference laboratory range will be used to determine the number and percentage of subjects who had shifts. Subjects with clinical laboratory values outside of the normal reference will be listed. The number and percentage as well as the listing of subjects who meet the criteria of Hy's law (with ALT or AST values \geq 3 times the ULN [$3 \times$ ULN] and total bilirubin \geq 2 times the ULN [$\geq 2 \times$ ULN]) will be summarized by post-baseline time point and treatment group.

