8.5.1 Close Observation and Clinical Management Plan

If early signs of possible DILI are detected in a subject, close observation should be initiated, and Sponsor should be notified within 24 hours (See protocol [Section 12.6.8](#)).

Clinical signs and symptoms of possible DILI or severe hepatotoxicity that may trigger close observation include, but are not limited to, the following:

- Persistent fatigue, weakness, nausea/vomiting, anorexia, pruritis, vague abdominal pain or right upper quadrant pain or tenderness, fever, rash, eosinophilia (eosinophils > 5%) in the absence of more likely causes
- Peripheral edema, ascites, encephalopathy, GI bleeding

- ALT > 3-fold ULN in subjects with normal baseline levels or 2-fold increases above baseline in subjects with abnormal levels prior to drug exposure

Close observation includes:

- Repeating liver enzyme and serum bilirubin tests 2 or 3 times weekly (the initial retest will occur within 48 hours). Frequency of retesting can decrease to once a week or less if abnormalities stabilize or the study drug has been discontinued and the subject is asymptomatic.
- Obtaining a more detailed history of symptoms and prior or concurrent diseases
- Obtaining a history of concomitant drug use (including nonprescription medications and herbal and dietary supplement preparations), alcohol use, recreational drug use, and special diets
- Ruling out acute viral hepatitis types A, B, C, D, and E; autoimmune or alcoholic hepatitis; NASH; hypoxic/ischemic hepatopathy; and biliary tract disease
- Obtaining a history of exposure to environmental chemical agents
- Obtaining additional tests to evaluate liver function, as appropriate (e.g., INR, direct bilirubin)
- Considering gastroenterology or hepatology consultations

Note that if additional testing is conducted, this information should be recorded in the eCRF.

Note: for any subject in whom a concern for hepatotoxicity or DILI develops (i.e., any subject that meets criteria for close observation), a narrative summary will be provided to the chairman of the DSMB by the Sponsor (via the CRO DSMB manager) for review by the board. The initial narrative summary will be provided within 24 to 48 hours of Sponsor notification of identifying a subject that meets the close observation criteria and updated versions provided as additional information becomes available and/or is requested by the DSMB chairman.

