8.5.2 Stopping Criteria

Stopping criteria for subject with elevated liver tests and relevant clinical signs and symptoms:

- ALT or AST $> 8 \times$ ULN
- ALT or AST $> 5 \times$ ULN for more than 2 weeks
- ALT or AST $> 3 \times$ ULN and total bilirubin $> 2 \times$ ULN or INR > 1.5
- ALT or AST $> 3 \times$ ULN with the appearance of fatigue, nausea, vomiting, right upper quadrant pain or tenderness, fever, rash, and/or eosinophilia (eosinophils $> 5\%$)

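### Outside the Hy's law count, Section 14.6.4 plans no by-arm table of ALT or AST at the multiples of ULN on which the protocol's own liver rules act

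*Combined protocol and SAP*

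**What the plan says.** Section 14.6.4 plans these laboratory displays by treatment group:

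- summary statistics for actual values and changes from baseline, with emphasis on the liver tests;
- out-of-range counts: "as well as numbers of subjects with values outside limits of the normal range at each time point";
- shift tables from baseline, for which "Normal reference laboratory range will be used to determine the number and percentage of subjects who had shifts";
- a listing of subjects with values outside the reference range;
- a Hy's law display: "The number and percentage as well as the listing of subjects who meet the criteria of Hy's law". This requires ALT or AST of at least 3 x ULN together with total bilirubin of at least 2 x ULN, and it "will be summarized by post-baseline time point and treatment group".

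The clinical sections use a finer scale. Section 8.5.1 includes among its close-observation triggers "ALT > 3-fold ULN in subjects with normal baseline levels", or a doubling over an abnormal pre-drug level. Section 8.5.2, headed "Stopping criteria for subject with elevated liver tests and relevant clinical signs and symptoms", lists ALT or AST above 8 x ULN; above 5 x ULN for more than 2 weeks; above 3 x ULN with total bilirubin above 2 x ULN or INR above 1.5; and above 3 x ULN with listed symptoms or eosinophilia.

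Section 14.1 defines baseline as the last measurement before first study drug. Table 1 (footnote m) and Section 10.2.3 place the baseline liver sample on postoperative Day 1, before dosing. One secondary objective (Section 6.1.2) reads: "Evaluate TU-100 compared with placebo with regards to the incidence and severity of hepatobiliary AEs".

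**The concern.** A normal-range table has one category for everything above ULN. The protocol treats 3, 5 and 8 x ULN as different clinical situations, but its by-arm tables do not separate them unless bilirubin is raised too. A reader of the planned tables could not count, by arm, how many subjects had an isolated transaminase rise large enough to reach the protocol's own thresholds.

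This matters because Section 5.4 gives systematic evaluation of possible drug-induced liver injury as the reason for close safety oversight, citing post-marketing surveillance in Japan. Subjects have also just had bowel resection. If mild transaminase rises from other causes are common, an excess of large rises on TU-100 would be mixed with them in a single above-normal count.

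The protocol takes a different approach for the ECG. Section 14.6.6 plans an outlier analysis on individual maxima, including repeat and unscheduled readings, with graded QTcF bands flagged on a listing. Section 14.6.4 has no counterpart for the liver tests.

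**Working it through.** The plan states no liver-table figure to reproduce, so the main check sets the rules beside the planned by-arm displays.

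**1. Is each liver criterion counted by arm in Section 14.6.4?**

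| Criterion | Section | By-arm count planned? |
|---|---|---|
| ALT > 3 x ULN, normal baseline | 8.5.1 | No |
| ALT doubled over an abnormal baseline | 8.5.1 | No |
| ALT or AST > 8 x ULN | 8.5.2 | No |
| ALT or AST > 5 x ULN for more than 2 weeks | 8.5.2 | No |
| ALT or AST > 3 x ULN and total bilirubin > 2 x ULN | 8.5.2 | Nearly: Hy's law count (at-least rather than above limits) |
| ALT or AST > 3 x ULN and INR > 1.5 | 8.5.2 | No |
| ALT or AST > 3 x ULN with symptoms or eosinophilia | 8.5.2 | No |

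One of the seven is covered, with slightly different inequalities.

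**2. What the shift table does with individual courses** (hypothetical subjects, Day 1 pre-dose baseline)

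| Day 1 ALT | Worst later ALT | Cell |
|---|---|---|
| normal | 1.1 x ULN | normal to high |
| normal | 9 x ULN | normal to high |
| 1.2 x ULN | 1.1 x ULN | high to high |
| 1.2 x ULN | 9 x ULN | high to high |

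Rows 1 and 2 cannot be told apart, nor can rows 3 and 4. The fourth subject passes the 8 x ULN level and is recorded as having no shift.

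**3. Time points.** After baseline, liver tests fall on Days 4, 7 and 10 if the subject is still in hospital, and on the day of discharge; the 30-day test is conditional on raised, falling values at discharge. Counts by time point therefore rest on whoever remains in hospital. No display takes each subject's worst value.

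**4. Direction of the dilution, on assumed rates.** The documents give no rates, so these inputs are assumptions. Let B be the proportion ever above ULN after baseline on placebo, and let e be the added proportion above 3 x ULN on one TU-100 dose, acting independently of B. Assume 1% of placebo subjects exceed 3 x ULN. With 134 per arm (Section 14.2):

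- expected number above ULN on TU-100 = 134 x [1 - (1 - B)(1 - e)]
- expected number above 3 x ULN on TU-100 = 134 x (0.01 + e), against 134 x 0.01 = 1.3 on placebo

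| e | > 3 x ULN, placebo v TU-100 | > ULN, B = 10% | > ULN, B = 30% | > ULN, B = 50% |
|---|---|---|---|---|
| 3 points | 1.3 v 5.4 | 13.4 v 17.0 | 40.2 v 43.0 | 67.0 v 69.0 |
| 5 points | 1.3 v 8.0 | 13.4 v 19.4 | 40.2 v 44.9 | 67.0 v 70.4 |
| 7 points | 1.3 v 10.7 | 13.4 v 21.8 | 40.2 v 46.8 | 67.0 v 71.7 |

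The excess in the above-ULN count is e(1 - B), so it shrinks as the background grows, while the count it is set against rises from 13 to 67. This shows the direction only; it does not estimate the effect in this trial.

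**The case against.** Several points on the other side are sound.

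- **Hy's law.** A reader might infer that no table compares the arms at 3 x ULN. That is wrong: the Hy's law count does so by time point and arm, but only for subjects who also meet the bilirubin limit.
- **Baseline.** A reader might argue from exclusion criterion 19, which requires transaminases no higher than ULN at screening, that nearly everyone starts in the normal row. The shift table starts from the Day 1 pre-dose sample, so a surgical rise already present that day is in the baseline row. That argument fails; the high-to-high problem takes its place.
- **Other displays.** Section 14.1 includes the maximum by treatment group, so a 9 x ULN value would be visible there, and out-of-range subjects are listed. But a maximum shows an extreme without counting subjects, and a listing is not a comparison of arms.
- **Adjudication.** Section 14.7.1 compares adjudicated hepatobiliary events across arms and makes that the primary evidence on liver-injury risk. The secondary objective concerns adverse events, so this is its main analysis and the laboratory tables are supportive. However, the adjudicated summary counts events, not ULN grades. Under Section 12.5 a laboratory result should be considered an adverse event when the investigator judges it clinically significant, so an isolated moderate rise need not appear.
- **Safety board narratives.** Section 8.5.1 sends a narrative on every close-observation subject to the board. That protects individuals but is not a tabulation by arm.
- **Deferral to the SAP.** Section 14.1 leaves data displays to a later SAP, which prevails where it differs. No separate SAP text is available here, so it may contain the missing table. It cannot be said that the trial will lack one. The normal-range rule in Section 14.6.4 nevertheless stands as written, and that section promises no further liver detail.

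**Conclusion.** The concern holds in a limited form. On the protocol text, liver-test shifts and out-of-range counts are classified against the normal range only. Apart from Hy's law, no by-arm table covers ALT or AST above 3, 5 or 8 x ULN, worst post-baseline values, or subjects meeting the close-observation or stopping criteria. The other displays narrow this gap without closing it.

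The size of any masking is unknown. A reader might infer from the structure that a TU-100 signal will be hidden; the documents do not support that, because they give no background or drug-related rate of liver-test elevation. The illustration rests on assumed rates and on independence between background and drug effect. No hypothesis test is planned for laboratory data, so the loss is one of descriptive resolution.

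The change should be made, given the stated interest in liver injury and the low cost. It does not affect the primary analysis or the sample size.

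**What to change.** In Section 14.6.4, and in the SAP if it is not already there, add a descriptive table by arm, and for the two TU-100 arms pooled (2 x 134 = 268 planned), showing:

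1. each subject's worst post-baseline ALT and worst post-baseline AST in the bands <=1, >1-3, >3-5, >5-8 and >8 x ULN;
2. the number and percentage with total bilirubin > 2 x ULN and with INR > 1.5;
3. the number and percentage meeting each close-observation criterion in Section 8.5.1 and each stopping criterion in Section 8.5.2, as written, including the doubling over an abnormal baseline.

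Use all scheduled, repeat and unscheduled values. Item 3 is needed because worst-value bands cannot reproduce the criteria that depend on duration, symptoms or a raised baseline. Keep the normal-range shifts as a supplement and the Hy's law display as it stands.

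The cost is one additional safety table from data already collected. No clinical rule, visit, sample or sample-size assumption changes.
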